### 4.3 Study Treatments

Subjects will be randomized 1:1 into 1 of 2 weekly treatment sequences:

**Sequence A:** 0.5 g/kg IgPro20 for 24 weeks (Study Period 1) followed by 0.5 g/kg IgPro20 for 28 weeks (Study Period 2) or

---

**Sequence B:** placebo for 24 weeks (Study Period 1) followed by 0.5 g/kg IgPro20 for 28 weeks (Study Period 2).

In Study Period 3, eligible subjects may continue treatment with SC infusions of open-label IgPro20 0.5 g/kg.

#### **4.4 Randomization Procedures and Blinding**

Eligible subjects will be randomized to 1 of the 2 double-blind treatment sequences by means of Interactive Response Technology (IRT). The IRT will assign the IMP to each subject and the correct dose volume based on the subject's body weight. Randomization will be done centrally and CSL Behring will supply the investigator with a user guide for the IRT.

Randomization will be stratified by region (Japan vs. non-Japan) and by MMT-8 assessment ( $\leq 142$  points vs.  $> 142$  points) to ensure even distribution of subjects to treatment sequences within stratum. For subjects with MMT-8 score at Baseline of  $\leq 142$  points and a muscle group not able to be assessed because of a non-DM related injury or an amputation, the Evaluating Physician will need to determine the appropriate stratification according to DM with muscle weakness (classic DM,  $\leq 142$  points) or DM with little or no muscle weakness (hypo / amyopathic DM,  $> 142$  points) and assign appropriate stratum for this subject.

The randomization list will be generated by the IRT external service provider according to the approved randomization specifications. The IRT external service provider will keep the randomization code on file.

Serum IgG levels will not be disclosed to the investigative site or any blinded study personnel before unblinding the study.

The study data will be unblinded for the primary data analysis (ie, end of Study Period 1 [EOP1] analysis) after all subjects have completed all assessments for Study Period 1 and the data has been cleaned for primary data analysis. CSLB site monitors, subjects and caregivers, as well as site personnel involved in the conduct of the study, will remain blinded to treatment allocation until all subjects have completed all assessments for Study Period 2.

---

## 4.5 Determination of the Sample Size

The study is designed as a superiority study. The sample size calculation is based on the hypothesis that IgPro20 will have a higher responder rate than placebo based on the TIS assessments at Weeks 17, 21, and 25.

A responder is defined as a subject with a TIS  $\geq 20$  points at Week 25 and at least on 1 of the previous scheduled visits (Week 17 or Week 21) who completes 24 weeks of IMP without the use of oral rescue corticosteroid treatment.

Two recent studies [[Aggarwal et al, 2018](#) and [Tjarnlund et al, 2018](#)] of subjects with DM or polymyositis (PM) reported the responder rates by the International Myositis Assessment and Clinical Studies Group (IMACS) definition of improvement. However, there are currently no data in the literature on the responder rates in the TIS for subjects with DM. For power simulation, it is assumed that 65% of subjects randomized to IgPro20 and 30% of subjects randomized to placebo have a TIS  $\geq 20$  points at Week 17. Further, it is assumed that for each subject, the response at Week 21 is conditional on the response at Week 17, and the response at Week 25 is conditional on the response at Week 21. Assumptions used are detailed in [Table 3](#).

**Table 3: Assumptions for Power Analysis**

Treatment Sequence A	Probability of having a TIS $\geq 20$ points at Week 17	Probability of having a TIS $\geq 20$ points at Week 21	Probability of having a TIS $\geq 20$ points at Week 25
A	65%	90%, if TIS $\geq 20$ points at Week 17	90%, if TIS $\geq 20$ points at Week 21
		20%, if TIS $< 20$ points at Week 17, or withdraw, or receive oral rescue corticosteroid treatment before Week 17	20%, if TIS $< 20$ points at Week 21, or withdraw, or receive oral rescue corticosteroid treatment before Week 21
B	30%	90%, if TIS $\geq 20$ points at Week 17	90%, if TIS $\geq 20$ points at Week 21
		10%, if TIS $< 20$ points at Week 17, or withdraw, or receive oral rescue corticosteroid treatment before Week 17	10%, if TIS $< 20$ points at Week 21, or withdraw, or receive oral rescue corticosteroid treatment before Week 21

A Treatment sequence A = 0.5 g/kg IgPro20 for 24 weeks followed by 0.5 g/kg IgPro20 for 28 weeks; Treatment sequence B = placebo for 24 weeks followed by 0.5 g/kg IgPro20 for 28 weeks.

Simulation shows a total of 126 subjects (63 subjects per treatment sequence) will be required for a power of 90% in 1-sided Fisher's exact test at a significance level of 0.025. Fisher's exact test is used in the power simulation as a close approximation to the exact logistic regression model in the primary endpoint analysis.

For further details see [Appendix 14.1](#).

## 4.6 Planned Interim Analyses and Reviews

### 4.6.1 Interim Analyses Other Than Sample Size Re-estimation

No analysis to stop for futility or other comparisons of treatment arms with respect to efficacy or safety at any time prior to the completion of the study is planned, except as described in Section [4.6.3](#).

The primary data analysis (EOP1 analysis) will be done after all subjects have completed all assessments for Study Period 1. At the time of the EOP1 analysis additional adverse event,

efficacy, and pharmacokinetic data of Study Period 2 will be analyzed. Efficacy analysis of the Study Period 2 data will be restricted to all subjects completing or discontinuing prematurely Study Period 2 at the time of data cut-off for the EOP1 analysis; the adverse events analysis will include all subjects treated in any study period at the time of data cut-off for EOP1 analysis; the pharmacokinetic analysis will include all subjects who have completed the rich PK sampling at Week 37.

Two additional analyses will be done after all subjects have completed all assessments for Study Period 2 (EOP2 analysis) and one after all subjects have completed all assessments for Study Period 3.

#### **4.6.2 Interim Sample Size Re-estimation**

Sample size re-estimation is not planned for this study.

#### **4.6.3 Independent Data Monitoring Committee (IDMC) Reviews**

The IDMC will monitor the efficacy and safety data generated during the Study Period 1 and 2 in order to conduct unblinded assessments of the benefit-risk profile. Data of Study Period 3 will not be reviewed by the IDMC. The composition, activities, and responsibilities of the IDMC will be described in the IDMC charter. The analyses to support the IDMC data review activities during the study will be detailed in a separate IDMC SAP.

### **5 Changes in the Conduct of Planned Analyses**

There were no changes to analyses planned in the study protocol.

### **6 Study Analysis Sets**

#### *Screened Analysis Set - SCR*

The SCR analysis set comprises all subjects who provided written informed consent and who undergo study Screening procedures.

#### *modified Intent-to-Treat Analysis Set - mITT*

The mITT analysis set is as complete and as close as possible to the Intent-to-Treat (ITT) principle. It comprises all subjects in the SCR who were randomized, met the major inclusion/exclusion criteria [ICH E9, 1998] and received any amount of randomized IMP. The

documented failure to take any amount of randomized IMP or the lack of any post randomization efficacy data will lead to the exclusion of the subject from the mITT. Documentation and final assessment will be done in the Blinded Data Review Meeting (BDRM). The mITT analysis will be based on the treatment sequence to which subjects were randomized.

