#### *Modified Intent-to-Treat Analysis Set – mITT*

The mITT analysis set is as complete and as close as possible to the Intent-to-Treat (ITT) principle. It comprises all subjects in the SCR who are randomized, meet the major inclusion/exclusion criteria and receive any amount of randomized IMP. The documented failure to take any amount of randomized IMP or the lack of any post randomization efficacy data in Study Period 1 [[ICH E9, 1998](#)] will lead to the exclusion of the subject from the mITT. Documentation and final assessment will be done in the Blinded Data Review Meeting (BDRM). The mITT analysis set will be based on the treatment sequence to which subjects is randomized.

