### 10.4.2.2 Primary Estimand

The primary interest is to quantify the treatment effect of IgPro20

- where the potential confounding effect of rescue corticosteroid treatment is excluded
- where the potential confounding of subjects who withdraw from treatment or withdraw from the study before Week 25 and cannot provide sufficient data to demonstrate a benefit of treatment is excluded, and
- in the absence of premature withdrawal from IMP or the study before Week 25 due to the Ukraine war [[EMA Biostatistics Working Party, 2022](#)].

The primary estimand in line with the primary interest of the study is described as follows:

- Population: the target patient population defined by eligibility criteria and who received any amount of randomized IMP treatment and have post baseline efficacy results in Study Period 1 (mITT). See [Section 10.3](#) for details.
- Variable: responder status based on TIS assessments at Weeks 17, 21, and 25
- Intercurrent events:
  - withdrawal from randomized IMP treatment or the study, which is not related to the Ukraine war, or receiving rescue corticosteroid treatment before Week 25 is considered treatment failure
  - withdrawal from IMP or the study that is related to the Ukraine war will be addressed using the hypothetical strategy [[Meyer et al, 2020; Collins et al, 2020](#)]
- Population-level summary: responder rate by treatment sequence

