### 10.4.2.3 Primary Efficacy Endpoint

The primary endpoint is the responder status in each treatment sequence based on TIS assessments at Weeks 17, 21, and 25. Following the estimand described in [Section 10.4.2.2](#), a responder is defined as a subject with a TIS  $\geq 20$  points at Week 25 and at least 1 of the previous scheduled visits (Week 17 or Week 21), who completes 24 weeks of randomized IMP treatment without the use of rescue corticosteroid treatment. Therefore, for subjects who do not withdraw from IMP or the study for reasons that are related to the Ukraine war before Week 25, non-responders will include subjects who meet any 1 of the following:

- TIS  $< 20$  points at Week 25
- TIS  $< 20$  points at both Weeks 17 and 21
- Withdraw from treatment or the study or receive rescue corticosteroid treatment before Week 25

To ensure that the treatment effect is not confounded by the intercurrent event of premature withdrawal from IMP or the study due to the Ukraine war, the hypothetical strategy is applied for this intercurrent event to quantify the treatment effect in the absence of the Ukraine war [[Meyer et al, 2020](#); [Collins et al, 2020](#)]. For subjects who do withdraw from IMP or the study for reasons which are related to the Ukraine war before Week 25, scheduled TIS assessments after withdrawal are missing. These missing values can be considered missing at random and multiple imputation will be used to derive the hypothetical post-intercurrent event TIS values and the corresponding response variables assuming that the subjects with missing TIS values continue in the same way as similar subjects in the study who did not withdraw prematurely. Multiple imputation is a simulation based approach where missing values are replaced by multiple Bayesian draws from the conditional distribution of missing data given the observed data and covariates, creating multiple completed data sets. The completed data sets can then be analyzed using standard methods (see [Section 10.4.2.3.1](#)). Note: If no TIS values are available for the subject for any post-randomization visit during Study Period 1, the subject will be excluded from the mITT analysis set (see [Section 10.3](#)).

Details of the multiple imputation process for TIS values and derivation of the responder status are provided below:

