## 8 Data Handling Conventions

### 8.1 Missing Data

#### 8.1.1 Imputation of Non-Date Missing Data

Per the protocol, subjects will be encouraged to remain in the study for the remainder of the phase during which they discontinue IMP, in order to collect further study assessments. Missing efficacy data will occur if a subject withdraws consent for additional post-discontinuation assessments. Below is how the missing efficacy data are handled in the key efficacy analyses:

- The primary endpoint analysis considers subjects discontinuing from the study before Week 25 as Non-responders, except for subject who discontinue due to the Ukraine war (see Section 10.2). This consideration is modified in the sensitivity analyses detailed in Section 10.2.1.
- The three continuous key secondary efficacy endpoints are analyzed with MMRM under the Missing at Random (MAR) assumption. No missing data imputation is required for this analysis approach.
- Tipping point analyses will be performed for the key secondary endpoint analyses.

The handling of missing data from questionnaires, CSMs, and other data collection instruments is described in the respective section of the specific instrument.

Subjects with the designation of relationship to IMP and/ or oral corticosteroid treatment for adverse events (AEs) and serious adverse events (SAEs) missing will have the worst case assumed to impute the relationship to IMP:

Relationship as entered in eCRF		Imputed relationship *	
to IMP	to oral corticosteroid treatment	to IMP	to oral corticosteroid treatment
missing	missing	related	not related
related	missing	related	not related
not related	missing	not related	related **
missing	related	not related	related
missing	not related	related	not related

\* Italic font is used for imputed values

\*\* Only if start of oral corticosteroid treatment was before or at start of AE, otherwise *not related*

There will be no other imputation for missing data other than as described in Section 8.1.2 for partial dates and times.

If the study is terminated early, all available data will be listed, and a review carried out by the study team to assess which statistical analyses are to be performed.

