### 10.1 Primary Estimand

The primary interest is to quantify the treatment effect of IgPro20

- where the potential confounding effect of oral rescue corticosteroid treatment is excluded
- where the potential confounding of subjects who withdraw from treatment or the study before Week 25 and cannot provide sufficient data to demonstrate a benefit of treatment is excluded, and
- in the absence of premature withdrawal from IMP or the study before Week 25 due to the Ukraine war [[EMA Biostatistics Working Party, 2022](#); [ICH E9 \(R1\), 2020](#)].

The primary estimand in line with the primary interest of the study is described as follows:

- Population: the target patient population defined by eligibility criteria and who received any amount of randomized IMP and have post baseline efficacy results in Study Period 1 (mITT). See Section 6 for details.
- Variable: responder status based on TIS assessments at Weeks 17, 21, and 25
- Intercurrent events:
  - withdrawal from randomized IMP or the study, which is not related to the Ukraine war, or receiving oral rescue corticosteroid treatment before Week 25 is considered treatment failure
  - withdrawal from randomized IMP or the study which is related to the Ukraine war will be addressed using the hypothetical strategy [Meyer et al, 2020; Collins et al, 2020].
- Population-level summary: responder rate by treatment sequence

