## 10.2 Analysis of Primary Endpoint

The primary endpoint is the responder status in each treatment sequence based on TIS assessments at Weeks 17, 21, and 25. Following the estimand described in Section 10.1, a responder is defined as a subject with a TIS  $\geq 20$  points at Week 25 and at least at 1 of the previous scheduled visits (Week 17 or Week 21) who completes 24 weeks of randomized IMP treatment without the use of oral rescue corticosteroid treatment.

Therefore, for subjects who do not withdraw from IMP or the study for reasons which are related to the Ukraine war before Week 25, non-responders will include subjects who meet any 1 of the following:

- TIS  $< 20$  points at Week 25
- TIS  $< 20$  points at both Weeks 17 and 21
- Withdraw from treatment or the study or receive oral rescue corticosteroid treatment before Week 25 (Note: for subjects with corticosteroid taper starting at Week 17, only an increase to doses greater than 125% of the Baseline corticosteroid dose following corticosteroid taper starting at Week 17 will be considered a “rescue” corticosteroid dose)

To ensure that the treatment effect is not confounded by the intercurrent event of premature withdrawal from IMP or the study due to the Ukraine war, the hypothetical strategy is applied for this intercurrent event to quantify the treatment effect in the absence of the Ukraine war [Meyer et al, 2020; Collins et al, 2020]. For subjects who withdraw from IMP or the study for reasons which are related to the Ukraine war before Week 25, scheduled TIS assessments after withdrawal are missing. These missing values can be considered missing at random (MAR) and multiple imputation will be used to derive the hypothetical post-intercurrent event TIS values and the corresponding response variables assuming that the subjects with missing TIS values continue in the same way as similar subjects in the study who did not withdraw prematurely. Multiple imputation is a simulation based approach where missing values are replaced by multiple Bayesian draws from the conditional distribution of missing data given the observed data and covariates, creating multiple completed data sets. The completed data sets can then be analyzed using standard methods. Note: If no TIS values are available for the subject for any post-randomization visit during Study Period 1, the subject will be excluded from the mITT analysis set (see Section 6).

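### The mITT drops dosed subjects with no post-baseline efficacy data, although two endpoints already score non-war withdrawal before Week 25 as failure

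*SAP*

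**What the plan says.** **Who is analysed.** SAP Section 6 defines the mITT as randomized, dosed subjects who meet the major eligibility criteria, and adds that the lack of any post "randomization efficacy data will lead to the exclusion of the subject from the mITT". Protocol Section 10.3 uses the same criterion, limited in time: "the lack of any post randomization efficacy data in Study Period 1". Final membership is settled in the Blinded Data Review Meeting. The population attribute of the primary estimand (SAP 10.1, Protocol 10.4.2.2) repeats the condition that post-baseline efficacy results exist.

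**How withdrawal is scored.** SAP 10.1 treats "withdrawal from randomized IMP or the study, which is not related to the Ukraine war", if it occurs before Week 25, as treatment failure. The non-responder list in SAP 10.2 makes such a withdrawal sufficient by itself. SAP 8.1.1 says the primary endpoint analysis "considers subjects discontinuing from the study before Week 25 as Non-responders, except for subject who discontinue due to the Ukraine war". Protocol 4.3.5 agrees, and neither section names a second exception. For the fourth key secondary endpoint, SAP 10.3 and Protocol 10.4.2.4.1 score non-war withdrawal as no reduction.

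**What is run.** Both endpoints are analysed in the mITT and repeated in the PP set, which is a subset of the mITT. The step in SAP 10.2 that adds withdrawn subjects to each imputed data set completes the mITT only. The sensitivity and supplementary analyses of the primary endpoint use the mITT and PP (SAP 10.2.1, Protocol 10.4.2.3.2).

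**The concern.** A lack-of-data exclusion makes sense where an outcome cannot be derived without data. Here it can. A subject who takes one infusion and leaves for a non-war reason is a failure under both endpoint rules, with or without a TIS or a steroid record. Removing that subject shrinks the denominator of two confirmatory tests by subjects who could only have been failures.

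If such losses are balanced, little happens. If more occur on IgPro20, the comparison tilts towards IgPro20. If more occur on placebo, it tilts against. The blinded review prevents selective choice of who is excluded, but it cannot correct an arm imbalance that the rule itself creates. SAP 9.1 lists excluded subjects, but no efficacy result is planned with them counted.

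**Working it through.** **Inputs.** 63 per arm, one-sided alpha 0.025 and Fisher's exact test (SAP 4.5). Conditional response probabilities come from SAP Table 3 and median responder rates from SAP Table 14. The documents give no number of dosed subjects without post-baseline data, so every removal count below is an assumption, written as IgPro20 vs placebo.

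**The plan's own power.** With r the Week 17 rate, c the chance of response after response and n the chance after non-response, the responder rate is r·c·c + r·(1−c)·n + (1−r)·n·c.

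- IgPro20: 0.65×0.9×0.9 + 0.65×0.1×0.2 + 0.35×0.2×0.9 = 0.6025
- Placebo: 0.30×0.9×0.9 + 0.30×0.1×0.1 + 0.70×0.1×0.9 = 0.309

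Full enumeration of Fisher's test at 63 vs 63 gives power 0.9037. Table 14 states 0.905, so the figure reproduces.

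**Observed data near the planned rates.** The Table 14 medians 0.603 and 0.317 correspond to 38/63 and 20/63. One-sided Fisher p:

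- none removed, 38/63 vs 20/63: 0.0011
- 4 vs 0 removed, 38/59 vs 20/63: 0.0003
- 0 vs 4 removed, 38/63 vs 20/59: 0.0030

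**Power and error.** If k non-responders are removed from an arm with rate p on all dosed subjects, responders in that arm follow Bin(63−k, p×63/(63−k)). For example, 0.31×63/59 = 0.331. Rejection means p ≤ 0.025.

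| Removed | Power at 0.6025 vs 0.309 | Error, 31% null on all dosed | Error, 31% null on retained |
|---|---|---|---|
| 0 vs 0 | 0.904 | 0.016 | 0.016 |
| 2 vs 2 | 0.907 | 0.016 | 0.016 |
| 4 vs 0 | 0.957 | 0.032 | 0.018 |
| 0 vs 4 | 0.828 | 0.008 | 0.015 |

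At the 31% null on all dosed subjects, 2 vs 0 gives 0.022 and 3 vs 0 gives 0.024, so the nominal level is passed only at an imbalance of about four. At a 20% null, five are needed (0.027). At a 40% null, 2 vs 0 already gives 0.027. With the null set on retained subjects, error stays between 0.015 and 0.018 in every scenario run.

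**Fourth key secondary endpoint.** The documents give no rate, so 10% to 40% is assumed. Error at 4 vs 0, against 0 vs 0: 0.017 vs 0.011 at 10%, 0.023 vs 0.015 at 20%, 0.031 vs 0.016 at 30%, 0.040 vs 0.018 at 40%.

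**A result near the limit.** This case is chosen to be borderline. 31/63 vs 20/63 gives p = 0.0345, and removing two IgPro20 failures (31/61) gives 0.0239. It also works in reverse: 32/63 vs 20/63 gives 0.0230, and removing one placebo failure (20/62) gives 0.0271.

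**The case against.** The best reply is that an analysis set says who is analysed and the endpoint rules say how those subjects are scored. The estimand states its population openly, and SAP 8.1.1 and Protocol 4.3.5 describe the primary endpoint analysis, which is the mITT analysis. Read that way, the texts are compatible. This largely stands: a reader might infer a flat contradiction, but the disclosed population does not support one. What remains is that the restriction discards outcomes the plan has already defined.

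The group may also be empty. Core set measures are due at the visit where treatment stops (Protocol 8.5.6, SAP 7.2), assessments are attempted at study withdrawal (Protocol 4.3.2.1), and subjects who stop treatment are encouraged to stay. Protocol Table 14, and Table 2 as far as it can be read, suggest these measures are taken at Week 2, although the Week 2 list in Section 8.5.3.2 omits them and they first appear in the Week 5 list. This stands as a limit on size. It does not close the route, because SAP 8.1.1 itself expects missing data when consent for later assessments is withdrawn.

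Two further inferences should be resisted. A reader might take the power simulation as proof that withdrawn subjects were meant to stay in the denominator as non-responders. SAP 14.1.1 describes it so, but Table 3 and the code give a withdrawn subject a 20% or 10% chance of response at the next visit, so the simulation cannot settle the question. A reader might also see a third exclusion criterion in the SAP 10.2 note: "If no TIS values are available for the subject for any post-randomization visit during Study Period 1, the subject will be excluded". That note closes the paragraph on war-related imputation, so its difference from the Section 6 wording is a minor harmonisation point.

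Finally, keeping these subjects puts two analysis populations inside one Hommel family. That is a real cost.

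**Conclusion.** The point holds as a misalignment between the analysis set and the failure rule of two confirmatory endpoints, with no planned analysis that shows the result with these subjects counted. Its expected numerical effect is small. At planned rates the conclusion does not change, and balanced loss does not raise error.

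The exclusion should not be read as inflating type I error in general. Under the assumptions used here, inflation needs a net excess of about four IgPro20 losses at a 31% null defined on all dosed subjects. It does not appear when the null is set on the retained subjects, which is the population the estimand names. The direction is unknown, and placebo losses would cost power.

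All figures rest on assumed removal counts and unadjusted Fisher tests, not the planned exact logistic regression pooled by Rubin's rule. The three MMRM endpoints are unaffected, because a subject with no post-baseline record adds no observation there. War-related withdrawals are also outside the point, because no failure rule applies to them. The correction is worth making because it is cheap and removes an avoidable source of bias.

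**What to change.** Before unblinding, state in SAP Section 6 and Protocol Section 10.3 that, for the primary and fourth key secondary endpoints, randomized and dosed subjects who meet the major eligibility criteria and withdraw before Week 25 for a non-war reason are kept as non-responders (or as no reduction), even with no post-baseline value. Make matching edits in SAP 10.1 to 10.4 and in Protocol 10.4.2.2 to 10.4.2.4.3, and say whether these subjects carry into the PP set. If only the SAP is amended, record the change in SAP Section 5, which now reports none. Use one wording of the lack-of-data criterion throughout.

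Leave the mITT as it is for the three MMRM endpoints and for war-related withdrawals with no post-baseline value. Run the present mITT as a sensitivity analysis for both endpoints, and report exclusions with reasons by arm.

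As a minimum, keep the present set as primary and add one sensitivity analysis per endpoint that counts the excluded non-war withdrawals as failures.

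The cost is wording, one extra model run per endpoint, two populations within the key secondary family, and possibly slightly lower responder rates. No new data or subjects are needed.
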